**E. TRALI AND TRANSFUSION EXPOSURE VALIDATION**

Medical records of all cases of inpatient diagnosis of TRALI will be reviewed, regardless of transfusion status or timing relative to transfusion. The maximum total number of cases to be reviewed is 200. If the available number of cases exceeds 200, we will use a pre-specified sampling scheme based on the diagnosis criteria to ensure that the highest-priority cases are reviewed.

Charts will be selected based on the following criteria:

1. All charts meeting Criterion A, identified in the time period of interest, will be reviewed
2. Charts meeting Criterion B or C, identified during the time period of interest, will be randomly selected for review, until a total of 200 charts is reached

The workgroup will collaborate with content experts to develop the chart abstraction/adjudication form to ensure all necessary information is collected from the medical records.

In order to identify the cases and obtain the medical charts, we will send programs for HCA to run on their uniform-format patient-level files. These programs will produce a report of the number and characteristics (e.g., age and sex) of the cases. The reports will include information on clinical setting, actual diagnosis, and date of the diagnosis. The list will be returned to HCA who will then attach patient name, HCA medical record number, and provider name and address to all visits. Another program to be run at HCA will organize the list of charts to pull by facility.

The chart of the entire hospitalization will be made available to clinicians who will abstract and adjudicate each case to verify the transfusion exposure and the TRALI diagnosis. Two clinicians will independently review 10 charts, blinded to the other reviewer’s decision. This initial round of case classification will enable refinement of the classification rules. Using the refined set of rules, the clinicians will complete a second round of case classification for another 10 cases. If discrepancies between reviewers are eliminated after the second round, then a single reviewer will be utilized for the

remainder of the cases. If discrepancies persist, additional rounds of double review may occur and could continue for the remainder of the case review.

Hospital care setting at the time of TRALI diagnosis (e.g., inpatient, institutional, outpatient, or emergency department), admission type (e.g., emergency, urgent, elective), hospital unit (e.g., coronary care unit, intensive care unit, trauma unit) will also be confirmed and recorded. Transfusion information in identified patients with TRALI will be reviewed to correctly identify the transfusion exposure. For patients with a prior transfusion identified in the HCA Sentinel database, the transfusion record prior to and closest to the TRALI event will be sought, to confirm or correct transfusion date and timing, number of transfused units for each blood component (e.g., RBCs, platelets, plasma, whole blood, autologous transfusion), volume of transfusion, type of blood component transfused, blood component processing (e.g., leukocyte reduced, irradiated) in the HCA Sentinel database. Hospital care setting for the time of transfusion exposure will also be confirmed. The indication for transfusion will be recorded for each patient if present. Use of mechanical ventilation before and after TRALI will also be confirmed. For patients without a prior transfusion recorded in the HCA Sentinel database, if the case is ultimately classified as TRALI, then HCA hospital records will be reviewed to attempt to confirm or correct the absence of a transfusion exposure prior to TRALI onset.

Clinicians will utilize the National Healthcare Safety Network (NHSN) Manual: Biovigilance Component definition of TRALI (summarized in **Table 1** and **Table 2** of this protocol) to diagnose TRALI. Delayed TRALI will be diagnosed in the same manner, but will allow for symptom onset between 6 and 72 hours of the transfusion. The primary analysis will be based on definitive TRALI, secondary analyses will include possible TRALI and delayed TRALI.

Positive predictive value will be determined for each electronic TRALI criterion as compared to definitive TRALI confirmed by clinical adjudicators. PPVs will also be calculated for each electronic TRALI criteria as compared to possible and delayed TRALI as confirmed by clinical adjudicators. The PPV will also be determined for the transfusion exposure as identified in HCA Sentinel data, as compared to confirmed transfusion exposure obtained by clinical adjudicators during chart review.

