## B. STUDY DESIGN AND OVERVIEW OF ANALYSIS PLAN

A retrospective cohort study design is proposed to examine TRALI occurrence among HCA patients transfused in a hospital inpatient setting between September 2013 and September 2015. Within this cohort, capture of potential TRALI cases, risk factors for TRALI, and relevant transfusion exposures in HCA’s Sentinel database will be described, and incidence rates of TRALI subsequent to plasma, platelet, packed red blood cell administration using HCA’s Sentinel database will be calculated. Medical chart reviews will be conducted to confirm the outcome (TRALI) and the transfusion exposure, and the positive predictive values of each electronic algorithm will be evaluated. The gold standard will be medical chart confirmed outcomes and transfusion exposures.

Unadjusted TRALI rates (per 100,000 inpatient transfusion stays) will be calculated overall, by year, blood component groups, sex, age, race, and number of units transfused. If appropriate transfused unit data are available, unadjusted TRALI rates per number of units transfused will also be calculated. Medical charts will be utilized to confirm the TRALI outcome and transfusion exposure in identified TRALI cases, and the positive predictive value of an ICD-9-CM based algorithm for identifying TRALI will be presented. Similarly, the positive predictive value of reported transfused product exposure and medical chart confirmed exposure in identified TRALI cases will be presented.

As HCA is a new Sentinel Data Partner, exploratory analyses are included as feasibility analyses (see page 2). The workgroup will explore the potential to compare blood component specific TRALI rates, examine TRALI patient and transfusion risk factors, and ability to identify specific categories of blood components, including component type and processing method (e.g., leukocyte-reduced, irradiated). Finally, the workgroup will describe which HCA data elements are included in the SCDM that are useful/relevant for studying TRALI, and which inpatient data elements could be useful but have not been included, and to assess the feasibility and need for adding these elements based on their availability, accuracy, and usefulness for blood and other biological products.

The plan is shown schematically below:

Relative Timing	Method	Analysis	Data to use

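### The chart review of transfusion exposure depends on the electronic record it is meant to validate, so the exposure PPV may be biased, most likely upward

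*Protocol*

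**What the plan says.** Two of the four primary objectives (section II.A, items 3 and 4) are validation measures: the performance of the code-based TRALI algorithm, and the PPV of the recorded product exposure in identified cases. Section IV.B sets the reference: "The gold standard will be medical chart confirmed outcomes and transfusion exposures".

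Section IV.E describes how that reference is obtained:

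- **Material.** "The chart of the entire hospitalization will be made available to clinicians who will abstract and adjudicate each case".
- **Masking.** "Two clinicians will independently review 10 charts, blinded to the other": each is kept unaware of how the colleague classified the case. A second round of 10 follows. "If discrepancies between reviewers are eliminated after the second round, then a single reviewer will be utilized for the": this covers all cases not yet read. No other masking is stated.
- **Exposure, transfusion on record.** The starting point is the database entry: "For patients with a prior transfusion identified in the HCA Sentinel database, the transfusion record prior to and closest to the TRALI event". The task is then defined by that entry, since the chart record "will be sought, to confirm or correct transfusion date and timing, number of transfused units for each blood component"; volume, component type and processing are treated likewise.
- **Exposure, none on record.** "if the case is ultimately classified as TRALI, then HCA hospital records will be reviewed to attempt to confirm or correct the absence": what is checked is whether the database was right to show nothing.
- **Exposure PPV.** The electronic exposure is assessed "as compared to confirmed transfusion exposure obtained by clinical adjudicators during chart review".

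Section IV.F.3.b adds that neither the electronic data nor the chart has fixed priority for transfusion timing; both are used to establish it.

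**The concern.** A validation study needs a reference that is set without regard to the value being tested. Here the exposure task is framed as checking a database entry, and the search differs according to what the database holds. A person asked to check a given value tends to let it stand when the source is unclear. The protocol itself expects unclear data: section IV.C warns of missing codes, codes of unknown validity and local coding habits.

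Timing raises the same problem. If electronic times help build the reference, agreement between electronic and reference times is partly agreement of a source with itself. Timing also decides case status, because the definitions in Table 1 turn on the interval between transfusion and onset. Electronic data can therefore enter the outcome reference as well.

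The outcome PPVs carry a related risk. They are reported separately for Criteria A, B and C. If a chart reviewer knows that the TRALI-specific code selected the chart, that knowledge could tip a borderline decision, and Table 1 leaves room for judgement (for example, hypoxemia shown by other clinical evidence).

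This is the first Sentinel use of the HCA data (section I), so an exposure PPV that is too high could be carried into later work.

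**Working it through.** The protocol gives no PPV, precision or sample-size figure on this point, so there is nothing to reproduce. The 200 charts in section IV.E are a cap. The check is a comparison of passages followed by an illustration on assumed values.

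**1. Is the reference independent of the index measure?**

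| Element | Section | Reading |
|---|---|---|
| Declared gold standard | IV.B | Chart |
| Exposure task, entry present | IV.E | Check and amend the database entry |
| Exposure task, entry absent | IV.E | Search only after a TRALI classification |
| Reference timing | IV.F.3.b | Chart and electronic data together |
| Masking | IV.E | Between reviewers, explicit for the first 10 charts; no role once one reviewer works alone |

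The second, third and fourth rows depart from the first, and the last row offers no protection against it.

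The rows act differently. A PPV is computed among electronic positives, so the entry-absent branch does not enter the exposure PPV directly. It bears on case classification, since every definition in Table 1 presupposes a transfusion. For the same reason, a PPV for any transfusion among confirmed cases is close to 1 by construction. The informative exposure PPVs are those for component, units and timing, where a check-and-amend task and shared timing can matter.

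**2. Size for exposure (assumed inputs)**

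Let p be the true PPV and f the share of false electronic entries that are wrongly confirmed. Then

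observed PPV = p + (1 − p) × f.

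| p | f = 0 | f = 0.10 | f = 0.25 | f = 0.50 |
|---|---|---|---|---|
| 0.80 | 0.80 | 0.82 | 0.85 | 0.90 |
| 0.90 | 0.90 | 0.91 | 0.925 | 0.95 |
| 0.95 | 0.95 | 0.955 | 0.9625 | 0.975 |

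Example: 0.80 + 0.20 × 0.50 = 0.90. The shift runs from 0 to 10 points.

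For scale, the 95% Wilson interval at an observed 0.80 is 0.739 to 0.850 with 200 cases and 0.711 to 0.867 with 100. Both counts are assumptions, as the protocol does not state how many cases will enter this PPV. The larger shifts are of the same order as sampling error, and no confidence interval would reveal them.

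**3. Size for the outcome (assumed inputs)**

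Suppose Criterion A and the others have the same true PPV p, and a share f of Criterion A non-cases is accepted because the code is known. The spurious gap is (1 − p) × f. At p = 0.5, f = 0.05, 0.10 and 0.20 give 2.5, 5 and 10 points. Over p = 0.3 to 0.7 the gap runs from 1.5 points (0.3 × 0.05) to 14 points (0.7 × 0.20).

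**The case against.** The strongest reply is that the text never puts the electronic values in the chart reviewer's hands. Section IV.E gives the clinicians the hospitalization chart. The case reports it describes list age and sex, setting, diagnosis and date, with no transfusion extract. Confirming or correcting may state only the purpose of a later comparison. Starting from recorded transfusions is inherent in a PPV. Component type and unit counts are fairly objective, and correction is expressly allowed. The abstraction form is still to be developed and could settle the matter.

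Much of this stands. A reader might infer that the chart reviewers are unmasked and that upward bias is established; the protocol is silent on what they see, so the bias is possible but not shown. A reader might also infer that a planned comparison of Criteria A, B and C is compromised. The protocol plans a descriptive PPV for each criterion and no formal comparison, and the qualifying diagnosis may be visible in the chart whatever is withheld. Nor can the bias be set against a stated uncertainty of the PPV, because the protocol states none.

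What the reply does not remove is the written procedure. The search depends on the database entry, the task is framed around that entry, and electronic timing is admitted to the reference. A later form would have to work within those instructions unless they are changed.

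**Conclusion.** The point holds as a weakness in a stated procedure. The reference for primary objective 4 is not independent of the electronic record, which sits badly with the chart gold standard of section IV.B. The exposure PPV for component, units and timing may be biased. Upward is the likelier direction, since anchoring mainly lets false entries stand. The criterion-specific outcome PPVs could be affected only if chart reviewers know the qualifying code, which the protocol leaves open.

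The size cannot be derived from the documents. With f between 0.10 and 0.50, the exposure PPV rises by 2 to 10 points at a true 0.80 and by 0.5 to 2.5 points at a true 0.95. With f = 0 it does not move. These rest on assumed p and f. The change is worth making because a better procedure is available at low cost.

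**What to change.** In section IV.E, replace the check-and-amend step with independent abstraction:

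1. Chart reviewers record the transfusions in the relevant window before onset (product, units, start and end time) from the chart, without the electronic transfusion values and with the same search whatever the database shows.
2. The form is locked. A program then matches it to the Sentinel transfusion record to give the exposure PPV.
3. The A/B/C label is withheld and chart order is mixed across criteria where feasible. The report states as a limitation that coded diagnoses may be visible in the chart.

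Reconcile section IV.F.3.b by admitting electronic timing only after locking. The exposure-timing comparison then uses chart-only times, and case classification is reported twice: with chart-only timing and with combined timing. This keeps the protocol's wish to use all timing data.

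The cost is a revised chart packet and form, a matching program and somewhat longer abstraction, because recording the transfusions in a window is more work than finding the single closest record. No additional charts are needed.

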## **F. STATISTICAL ANALYSIS**

### **1. Descriptive Analyses**

A number of univariate and bivariate descriptive analyses in the form of tables, histograms, and other graphs will be carried out prior to calculating rates of TRALI in order to characterize the transfusion and TRALI data in HCA's Sentinel database. These will include frequency distributions of TRALI cases meeting each TRALI electronic criterion, and frequency distributions of relevant transfusion variables including any relevant missing information. Codabar and ISBT Coding systems utilized by HCA to identify plasma, platelets and packed red blood cells will be explored. The number of potential TRALI inpatient transfusion stays will be identified, and frequencies of specific blood component exposure among inpatient transfusions stays will be presented. If feasible, patient (e.g., smoking status, alcohol abuse, direct lung injury, indirect lung injury, diabetes, COPD, chemotherapy or malignancy) and transfusion (e.g., number of units, blood component transfused) level risk factors of interest will be examined.

Descriptive analyses will also be used to examine TRALI case demographics and patient and transfusion risk factors of interest.

## 2. Calculation of Incidence Rates

Unadjusted incidence rates of TRALI occurrence after any transfusion will be calculated, along with 95% confidence intervals. Any transfusion will be defined as exposure to plasma, platelets (PLT), or packed red blood cells (RBC) as defined in HCA's Sentinel database. TRALI will be defined using ICD-9-CM based codes in HCA's Sentinel database, and the primary analysis will focus on TRALI as defined by criterion A (Table 5). Unadjusted TRALI rates (per 100,000 inpatient transfusion stays) will be stratified by year, blood component groups (i.e., plasma, PLT, and RBC), age, sex, race, and quantified units. If data on the number and type of component unit(s) transfused are available, unadjusted TRALI rates per number of units transfused will also be calculated. If feasible, quantified units will be examined separately for children and adults.

In addition to identifying rates of TRALI occurrence after any exposure to plasma, PLT, or RBC during an inpatient stay, if adequate sample size is available we will also explore exposure to RBC-only, plasma-only, and PLT-only. Exposure to multiple blood component types (i.e., plasma and PLT, RBC and PLT, plasma and RBC, plasma and RBC and PLT) or non-specific blood components (if relevant) will also be described.

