Initial	Descriptive analysis examining capture of potential TRALI cases, risk factors for TRALI, and relevant transfusion exposures	Primary	Transfusions: HCA Sentinel Data Outcome: HCA Sentinel Data
	Descriptive analyses, examining potential to compare blood component specific TRALI unadjusted rates	Exploratory	Transfusions: HCA Sentinel Data Outcome: HCA Sentinel Data
	Descriptive analyses, examining: 
 
ability to identify specific categories of blood components, including component type and processing method (e.g., leukocyte-reduced, irradiated)
 
methods for reducing any relevant missing transfusion information in HCA’s Sentinel database
 
distribution of possible patient risk
 
	Exploratory	Transfusions: HCA Sentinel Data Outcome: HCA Sentinel Data

Relative Timing	Method	Analysis	Data to use
	
factors, such as age, sex, and relevant comorbidities, among cases of TRALI
 
 
distribution of possible transfusion risk factors, such as volume of transfusion, indication, pregnancy history, component processing (e.g., leukoreduction, irradiation) among cases of TRALI
 
transfusion stays with TRALI vs without TRALI, comparing demographic characteristics (age, gender, race), length of stay, mechanical ventilation (identified with ICD-9-CM procedure codes) and inpatient mortality
 
		
Final	Descriptive analysis, calculating unadjusted rates of TRALI in identified cohort	Primary	Transfusions: HCA Sentinel Data Outcome: HCA Sentinel Data
	Validation of TRALI outcome, in identified TRALI cases	Primary	Transfusions: HCA Sentinel Data Outcome: HCA Sentinel Data and Chart Review
	Validation of transfusion exposure in identified TRALI cases	Primary	Transfusions: HCA Sentinel Data Outcome: HCA Sentinel Data and Chart Review
	Descriptive analysis identifying which HCA data elements are included in the SCDM that are useful/relevant for studying TRALI, and which inpatient data elements could be useful but have not been included, and to assess the feasibility and need for adding these elements based on their availability, accuracy, and usefulness for blood and other biological products	Exploratory	Transfusions: HCA Sentinel Data Outcome: HCA Sentinel Data

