**Table 5: Electronic criteria to identify potential cases of TRALI**

Criteria	ICD-9-CM Code(s)
Criterion A	TRALI, ICD-9-CM code in any position (518.7)
Criterion B	Acute respiratory failure ICD-9-CM code in any position (518.81), WITH code for a blood transfusion reaction (999.80 or 999.89 or E934.7)
Criterion C	Other pulmonary insufficiency (518.82), WITH code for a blood transfusion reaction (999.80 or 999.89 or E934.7)
Any TRALI Criteria	Criteria A, and/or B, and/or C listed above

The above criteria and codes will be used to identify TRALI cases in HCA’s Sentinel database and will be used to calculate incident rates of TRALI subsequent to plasma, platelet and packed red blood cell administration based on the electronic criteria. Stratifications will be made by TRALI criterion as feasible. These TRALI criteria will also be used to identify TRALI cases in HCA’s Sentinel database for chart review.

Medical charts will be obtained for relevant cases, reviewed and adjudicated by clinical experts.

This chart information will identify chart validated cases, which will be the gold standard for the primary validation objective. Please see section E.

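### The primary TRALI rate counts every transfused stay coded 518.7, and no rate is planned on chart-confirmed cases although all Criterion A charts are adjudicated

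*Protocol*

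**What the plan says.** Objective 2 asks for incidence rates of TRALI after transfusion. Three places fix how the numerator is counted:

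- Section IV.D, after Table 5: the electronic criteria "will be used to calculate incident rates of TRALI subsequent to plasma, platelet and packed red blood cell administration based on the electronic criteria".
- Section IV.F.2: "the primary analysis will focus on TRALI as defined by criterion A (Table 5". Table 5 defines that criterion as "TRALI, ICD-9-CM code in any position (518.7", with no clinical condition attached.
- The schematic in section IV.B, Final stage: the primary row "Descriptive analysis, calculating unadjusted rates of TRALI in identified cohort" takes its outcome from the HCA Sentinel data alone. The two validation rows beside it add chart review.

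On the charts, section IV.B states: "The gold standard will be medical chart confirmed outcomes and transfusion exposures". Section IV.E states: "All charts meeting Criterion A, identified in the time period of interest, will be reviewed". The adjudications then feed a PPV for each criterion (IV.E and IV.F.3). Section IV.E also contains this sentence: "The primary analysis will be based on definitive TRALI, secondary analyses will include possible TRALI and delayed TRALI". It does not say which analysis is meant.

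**The concern.** Criterion A and definitive TRALI are different things. A 518.7 code in any position carries no requirement on onset time, oxygenation, imaging, circulatory overload or competing causes of lung injury. Table 1 requires all of these for a definitive case. The coded numerator can therefore mix definitive, possible and delayed TRALI with stays that are none of them.

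The study will hold an adjudicated status for each Criterion A case whose chart is obtained, but as written it never uses that status in the rate. The 95% confidence interval on the coded rate reflects sampling error only and can exclude the confirmed rate altogether. The stratified rates (year, component, age, sex, race, units) and the exploratory rate ratios of IV.F.4 inherit the problem. If the code is less reliable in one stratum than in another, part of the apparent difference is a coding artefact.

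**Working it through.** **Can every Criterion A chart be reviewed?** Section IV.E sets a limit: "The maximum total number of cases to be reviewed is 200". Section IV.F.5 expects fewer than 200 cases. That expectation cannot be reproduced, because the share of stays with a transfusion is not given, but its plausibility can be checked.

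- Inputs: about 2 million inpatient encounters a year (III.B); September 2013 through September 2015, 25 months (IV.A); 22.5 per 100,000 transfused stays, from a study in elderly Medicare beneficiaries (III.D), used here only as an illustration.
- Encounters: 2,000,000 × 25/12 = 4.17 million.
- With an assumed transfused share of 5% to 15%: 208,333 to 625,000 transfused stays, hence 47 to 141 cases.
- To reach 200 cases: 200 / 0.000225 = 888,889 transfused stays, a share of about 21%.

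So fewer than 200 is plausible, and the cap should not prevent full review of Criterion A.

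**Coded against confirmed rate.** Among transfused stays coded 518.7, confirmed rate = coded rate × PPV, so coded / confirmed = 1/PPV. The protocol states no PPV, so the values below are assumptions. Take a coded rate of 22.5 per 100,000 and 100 coded cases in 100 / 0.000225 = 444,444 stays. The exact Poisson 95% interval for the coded rate is then 18.3 to 27.4.

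| Assumed PPV | Confirmed rate per 100,000 | Exact 95% CI | Coded / confirmed |
|---|---|---|---|
| 0.9 | 20.3 | 16.3–24.9 | 1.11 |
| 0.7 | 15.8 | 12.3–19.9 | 1.43 |
| 0.5 | 11.3 | 8.3–14.8 | 2.00 |
| 0.3 | 6.8 | 4.6–9.6 | 3.33 |

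In this illustration the coded interval excludes the confirmed point estimate once the PPV falls below 18.3/22.5 = 0.81. At a PPV of 0.5 the two intervals do not overlap.

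**Coded rate against true incidence.** Here coded / true = sensitivity/PPV. With sensitivity 0.5 and PPV 0.9 the ratio is 0.56; with 0.5 and 0.5 it is 1.00; with 0.9 and 0.3 it is 3.00. No charts without the codes are reviewed, so sensitivity cannot be estimated. Section IV.D itself expects under-diagnosis. The coded rate may be too low, about right or too high.

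**Can a reader simply multiply by the reported PPV?** Not safely. Section IV.E reviews charts whatever the transfusion status, while the rate counts transfused stays. Suppose 100 Criterion A charts, of which 20 have no transfusion record and none of those 20 is confirmed, while 40 of the other 80 are confirmed. The overall PPV is 40/100 = 0.40, implying a factor of 2.5. The factor that applies to the rate is 80/40 = 2.0.

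**Strata.** If two strata have the same confirmed rate but PPVs of 0.6 and 0.3 (assumed), their coded rates differ by a factor of 0.6/0.3 = 2.

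**The case against.** The protocol is open about its code basis. Objective 2 refers to the Sentinel database, IV.D names the electronic criteria, the work is presented as a feasibility assessment, and IV.F.5 expects the analyses to be descriptive. The PPV is itself a primary deliverable, so a reader could approximate the overall confirmed rate. The background rate of 22.5 comes from a study whose title in the reference list says it used Medicare claims, so a code-based rate is the natural comparator. An analysis plan, not shown, could add the confirmed rate later without new data.

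Much of this stands. It is a good reason to keep the coded rate and to regard the omission as repairable. It does not remove the gap. The protocol specifies a code-only rate in three places, so an analysis plan that followed it would produce only that. The reported PPV is not restricted to the cases in the rate, and IV.F.3 only considers stratifying it, by age and gender. Component, race, year and unit strata would have no confirmed counterpart.

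A reader might infer three stronger claims that the document does not support:

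- *That the headline rate misstates TRALI incidence by 1/PPV.* That factor applies only against the confirmed rate among coded transfused stays. The confirmed rate also omits uncoded cases, and it could lie further from true incidence than the coded rate does. With sensitivity and PPV both 0.5, the coded rate equals true incidence and the confirmed rate is half of it.
- *That the exploratory case descriptions ignore the charts.* The schematic lists electronic data for them, but IV.A says chart information will inform the explorations, and IV.F.3 collects chart data for them.
- *That IV.E and IV.F.2 flatly contradict each other on the primary analysis.* The IV.E sentence directly precedes the PPV text and most naturally means the PPV analysis. Read literally it conflicts with IV.F.2, so it needs clarifying.

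**Conclusion.** The concern holds in limited form. The primary rate is a rate of coded TRALI, and the plan omits the chart-confirmed rate that its own adjudication makes possible. The coded rate exceeds the confirmed rate among coded transfused stays by 1/PPV. That is 1.1 to 3.3 for PPVs of 0.9 to 0.3, all of them assumed; the true size will be known only after chart review. The direction and size of the error against true incidence cannot be determined. The stratum distortion is a possibility that depends on PPV differing between strata, and the rate ratios it would affect are exploratory and conditional on feasibility. This should be fixed before analysis, because it changes what Objective 2 can conclude. It does not threaten the data collection.

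**What to change.** In IV.F.2 and in the Final-stage rate row of the IV.B schematic:

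1. Keep the code-based rate and label it as the rate of coded TRALI.
2. Report beside it the rate of Criterion A stays with a recorded transfusion that are adjudicated definitive, then adding possible, then adding delayed. Express it per 100,000 transfused stays, overall and by stratum, with exact Poisson 95% intervals.
3. If some charts cannot be obtained, multiply the coded rate by the PPV estimated only among Criterion A transfused stays, and carry both variances into the interval. With D coded cases, n reviewed charts and PPV p, the variance of the log rate is approximately 1/D + (1 − p)/(np). When n = D this reduces to 1/(Dp), the usual Poisson value for the confirmed count.
4. State that neither rate corrects for missed cases.
5. Say in IV.E and IV.F.2 which analysis each statement of the primary analysis refers to.

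The cost is a few sentences and some extra table columns. No further charts are needed. The confirmed rate will be no higher than the coded rate and relatively less precise, and some strata may have very few confirmed cases.
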